5.5.3 Description of the health status of GCA patients

The following data will be presented:

- SF-36 questionnaire

The SF-36 is a self-report, 36 item survey measuring health-related quality-of-life. The SF-36 consists of eight scaled scores. A score ranging from 0 (indicating the worse health status) to 100 (indicating the best health status) is assigned for each domain.

Scoring and handling missing data of the SF-36 will be performed by Optium's scoring solution software. This software is provided now with the licence of the SF-36v2 survey and allows to score data from SF36v2 with high accuracy. Only 300 questionnaires with the fewest missing data will be analyzed

In case of double answer or more, the question will be considered as missing data.

The proportion of patients having completed the SF-36 questionnaire will be presented.

Then for patients who have completed SF-36 questionnaire, total scores for each of the eight health domains and psychometrically-based physical component summary (PCS) and mental component summary (MCS) scores will be provided by Optium's scoring solution software.

The score for each item of SF-36 will be presented (as qualitative variables) as well as the total score for each domain (as quantitative variables). Psychometrically-based physical component summary (PCS) and mental component summary (MCS) scores will be also presented as quantitative variables.

- EQ5D-3L questionnaire

The EQ5D-3L consists of five questions relating to five dimensions of health. Respondents indicate which of a possible three statements best describe their current health state for each dimension. Each

dimension has 3 levels: no problems, some problems, extreme problems. Respondents are asked to repeat this process for the five dimensions by indicating one level for each dimension, giving rise to scores ranging from 1 to 3, with scores of 3 on each dimension indicating the most severe impairment. Binary variables will be computed for each dimension dichotomising the levels into 'No problems' (level 1) and 'Problems' (levels 2 and 3). Perceived current health state will be measured by asking respondents to indicate their current health state on a VAS with endpoints labelled 0 'Worst imaginable health state' and 100 'Best imaginable health state'.

In case of double answer or more, the question will be considered as missing data.

The proportion of patients having completed the EQ5D-3L questionnaire will be presented.

Then for patients who have completed the EQ5D-3L, the score for each item of EQ5D-3L will be presented (in qualitative variable at 2 and 3 modalities for the 5 dimensions and in quantitative for VAS).

- FACIT-Fatigue

The proportion of patients having completed the FACIT_Fatigue questionnaire will be presented.

In case of double answer, the question will be considered as missing data.

If FACIT_Fatigue questionnaire was completed, the score for each items of FACIT-Fatigue (13 items) will be presented (as qualitative variable) as well as the total score (quantitative variable). ([APPENDIX](#))

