15 APPENDICES

15.1 Appendix 1: 36-Item Short Form Survey Instrument (SF-36)

RAND 36-Item Health Survey 1.0 Questionnaire Items

Choose one option for each questionnaire item.

1. In general, would you say your health is:

- 1 - Excellent
- 2 - Very good
- 3 - Good
- 4 - Fair
- 5 - Poor

2. **Compared to one year ago**, how would you rate your health in general **now?**

- 1 - Much better now than one year ago
- 2 - Somewhat better now than one year ago
- 3 - About the same
- 4 - Somewhat worse now than one year ago
- 5 - Much worse now than one year ago

CHUGAI PHARMA FRANCE
CPF - Artemis - Protocol - Version 1.3 17-09-2018.docx

The following items are about activities you might do during a typical day. Does **your health now limit you** in these activities? If so, how much?

	Yes, limited a lot	Yes, limited a little	No, not limited at all
3. Vigorous activities , such as running, lifting heavy objects, participating in strenuous sports	 1	 2	 3
4. Moderate activities , such as moving a table, pushing a vacuum cleaner, bowling, or playing golf	 1	 2	 3
5. Lifting or carrying groceries	 1	 2	 3
6. Climbing several flights of stairs	 1	 2	 3
7. Climbing one flight of stairs	 1	 2	 3
8. Bending, kneeling, or stooping	 1	 2	 3
9. Walking more than a mile	 1	 2	 3
10. Walking several blocks	 1	 2	 3
11. Walking one block	 1	 2	 3
12. Bathing or dressing yourself	 1	 2	 3

During the **past 4 weeks**, have you had any of the following problems with your work or other regular daily activities **as a result of your physical health?**

	Yes	No
13. Cut down the amount of time you spent on work or other activities	 1	 2
14. Accomplished less than you would like	 1	 2

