26. Have you felt calm and peaceful?	 1	 2	 3	 4	 5	 6
27. Did you have a lot of energy?	 1	 2	 3	 4	 5	 6
28. Have you felt downhearted and blue?	 1	 2	 3	 4	 5	 6
29. Did you feel worn out?	 1	 2	 3	 4	 5	 6
30. Have you been a happy person?	 1	 2	 3	 4	 5	 6
31. Did you feel tired?	 1	 2	 3	 4	 5	 6

32. During the **past 4 weeks**, how much of the time has **your physical health or emotional problems** interfered with your social activities (like visiting with friends, relatives, etc.)?

- 1 - All of the time
- 2 - Most of the time
- 3 - Some of the time
- 4 - A little of the time
- 5 - None of the time

How TRUE or FALSE is **each** of the following statements for you.

	Definitely true	Mostly true	Don't know	Mostly false	Definitely false
33. I seem to get sick a little easier than other people	 1	 2	 3	 4	 5
34. I am as healthy as anybody I know	 1	 2	 3	 4	 5
35. I expect my health to get worse	 1	 2	 3	 4	 5
36. My health is excellent	 1	 2	 3	 4	 5

RAND® is a registered trademark. Copyright © 1994-2016 RAND Corporation.

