Q3h. Walking several blocks Yes, Limited a Lot Yes, Limited a Little No, Not limited at All	n(%) n(%) n(%) Filled, n(%) Missing, n(%)	
Q3i. Walking one block Yes, Limited a Lot Yes, Limited a Little No, Not limited at All	n(%) n(%) n(%) Filled, n(%) Missing, n(%)	
Q3j. Bathing or dressing yourself Yes, Limited a Lot Yes, Limited a Little No, Not limited at All	n(%) n(%) n(%) Filled, n(%) Missing, n(%)	
Q4a. Cut down the amount of time you spent on work or other activities All of the time Most of the time Some of the time A little of the time None of the time	n(%) n(%) n(%) n(%) n(%) Filled, n(%) Missing, n(%)	
Q4b. Accomplished less than you would like All of the time Most of the time Some of the time A little of the time None of the time	n(%) n(%) n(%) n(%) n(%) Filled, n(%) Missing, n(%)	
Q4c. Were limited in the kind of work or other activities All of the time Most of the time Some of the time A little of the time None of the time	n(%) n(%) n(%) n(%) n(%) Filled, n(%) Missing, n(%)	
Q4d. Had difficulty performing the work or other activities (for example, it took extra effort) All of the time Most of the time Some of the time A little of the time None of the time	n(%) n(%) n(%) n(%) n(%)	

Table 28 - Descriptive analysis - SF-36 Quality of life questionnaire- Analysis population (N=XX)

	Filled, n(%) Missing, n(%)	
Emotional role functioning:		
During the past 4 weeks, have you had any of the following problems with your work or other regular daily activities as a result of any emotional problems (such as feeling depressed or anxious)?		
Q5a. Cut down the amount of time you spent on work or other activities		
All of the time	n(%)	
Most of the time	n(%)	
Some of the time	n(%)	
A little of the time	n(%)	
None of the time	n(%)	
	Filled, n(%)	
	Missing, n(%)	
Q5b. Accomplished less than you would like		
All of the time	n(%)	
Most of the time	n(%)	
Some of the time	n(%)	
A little of the time	n(%)	

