Q9d. Have you felt calm and peaceful? All of the time Most of the time Some of the time A little of the time None of the time	n(%) n(%) n(%) n(%) n(%) Filled, n(%) Missing, n(%)	
Q9e. Did you have a lot of energy? All of the time Most of the time A good bit of the time Some of the time A little of the time None of the time	n(%) n(%) n(%) n(%) n(%) n(%) Filled, n(%) Missing, n(%)	
Q9f. Have you felt downhearted and blue? All of the time Most of the time Some of the time A little of the time None of the time	n(%) n(%) n(%) n(%) n(%) Filled, n(%) Missing, n(%)	
Q9g. Did you feel worn out? All of the time Most of the time A good bit of the time Some of the time A little of the time None of the time	n(%) n(%) n(%) n(%) n(%) n(%) Filled, n(%) Missing, n(%)	
Q9h. Have you been a happy person? All of the time Most of the time Some of the time A little of the time None of the time	n(%) n(%) n(%) n(%) n(%) Filled, n(%)	

Table 28 - Descriptive analysis - SF-36 Quality of life questionnaire- Analysis population (N=XX)

	Missing, n(%)	
Q9i. Did you feel tired? All of the time Most of the time A good bit of the time Some of the time A little of the time None of the time	n(%) n(%) n(%) n(%) n(%) n(%) Filled, n(%) Missing, n(%)	
Q10. During the past 4 weeks, how much of the time has your physical health or emotional problems interfered with your social activities (like visiting with friends, relatives, etc.)? All of the time Most of the time Some of the time A little of the time None of the time	n(%) n(%) n(%) n(%) n(%) Filled, n(%) Missing, n(%)	
Q11a. I seem to get sick a little easier than other people Definitely true Mostly true Don't know Mostly false Definitely false	n(%) n(%) n(%) n(%) n(%) Filled, n(%) Missing, n(%)	

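### Protocol and SAP do not agree on which SF-36 form is used (response levels differ for 12 of 36 items), and the SAP limits the SF-36 analysis to the 300 most complete forms; neither is declared as a change

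*SAP*

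**What the plan says.** **Instrument.** Protocol 5.3.2.1 refers the reader to Appendix 1 for the SF-36. That appendix is headed "RAND 36-Item Health Survey 1.0 Questionnaire Items". Its items 13 to 19 are answered Yes or No, and its items 23 to 31 share a single six-level scale. The SAP names a different version. Section 5.5.3 hands scoring and missing-item handling to licensed software and states: "This software is provided now with the licence of the SF-36v2 survey and allows to score data from SF36v2 with high accuracy". The eight domain scores and the physical and mental component summaries (PCS, MCS) are to come from that software.

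**Analysis set.** SAP 5.5.3 adds: "Only 300 questionnaires with the fewest missing data will be analyzed". SAP 4 defines the Analysis Population as all eligible included patients, with no condition on questionnaires. SAP 5.5 and Protocol 7.2.3 place the secondary objectives on that population, and the titles of SAP Tables 28 and 29 carry the same label. For SF-36 missing data, Protocol 7.2.3.2 relies on the user's manual and mentions no selection of forms.

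**Declared changes.** SAP 5.6 lists one departure from the protocol, on treatments for glucocorticoid-related comorbidities. It does not mention the SF-36.

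**The concern.** The SF-36 is one of three patient-reported instruments serving the health-status secondary objective. A programmer working from the two documents cannot tell which response codes and which scoring key apply to a third of the items. A Yes/No answer carries less information than a five-level answer and cannot be fed to a five-level key as it stands. If the form and the key do not match, the role domains fail, and so do the component summaries reported with them.

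The 300-form rule raises a different question: which patients the SF-36 tables describe. It selects on completeness, which may be related to health, age or fatigue. EQ-5D-3L and FACIT-Fatigue have no such limit. If the rule acts, the three instruments would be reported on different patients under the same population label.

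**Working it through.** **1. Response levels, item by item.** Inputs are the answer options printed in Protocol Appendix 1 and those listed in SAP Table 28.

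| Appendix 1 items | Table 28 rows | Levels, Appendix 1 | Levels, Table 28 | Items that differ |
|---|---|---|---|---|
| 1–2 | Q1–Q2 | 5 | 5 | 0 |
| 3–12 | Q3a–j | 3 | 3 | 0 |
| 13–16 | Q4a–d | 2 | 5 | 4 |
| 17–19 | Q5a–c | 2 | 5 | 3 |
| 20, 21, 22 | Q6, Q7, Q8 | 5, 6, 5 | 5, 6, 5 | 0 |
| 24, 25, 26, 28, 30 | Q9b, c, d, f, h | 6 | 5 | 5 |
| 23, 27, 29, 31 | Q9a, e, g, i | 6 | 6 | 0 |
| 32 | Q10 | 5 | 5 | 0 |
| 33–36 | Q11a–d | 5 | 5 | 0 |

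Items that differ: 4 + 3 + 5 = 12, and 12/36 = 33.3%. All seven role items are among them.

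Two rows can be checked directly. "13. Cut down the amount of time you spent on work or other activities" is Yes/No in Appendix 1, while "Q4a. Cut down the amount of time you spent on work or other activities" has five frequency levels in Table 28. "26. Have you felt calm and peaceful" has six levels in Appendix 1, while "Q9d. Have you felt calm and peaceful" has five in Table 28.

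**2. What the count measures.** It compares Appendix 1 with the Table 28 shell. Within Q9, Table 28 gives five levels to five items and six levels to four, whereas Appendix 1 uses one scale for all nine. No SF-36v2 form is reproduced in either document, so 12 is not a count of the differences between two versions of the instrument.

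**3. Fit of the role items.** With k items of L levels each, the number of distinct raw sums is k(L − 1) + 1.

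- Four physical-role items: 4 × 1 + 1 = 5 sums with Yes/No answers, 4 × 4 + 1 = 17 with five levels.
- Three emotional-role items: 3 × 1 + 1 = 4 sums, against 3 × 4 + 1 = 13.

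Yes/No answers therefore do not fill the scale that Table 28 sets out. No conversion rule is given. The size of any scoring error cannot be computed, because neither document gives the item codes or the key.

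**4. The two branches.**

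- Patients complete the Appendix 1 form: v2 scoring does not fit the role items, the five-level Q9 rows do not fit the six-level answers, and the affected domain scores and PCS/MCS would be invalid.
- Patients complete v2: Appendix 1 shows the wrong form, and the six-level Q9 rows of Table 28 must be checked against the form used.

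**5. The 300-form rule.** Planned enrolment is 300 (Protocol 4.2). With N returned forms, the share dropped is max(0, N − 300)/N. N is not given, so the values below are assumptions.

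| N returned (assumed) | Dropped | Share |
|---|---|---|
| 300 or fewer | 0 | 0% |
| 310 | 10 | 3.2% |
| 320 | 20 | 6.3% |
| 350 | 50 | 14.3% |
| 400 | 100 | 25.0% |

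The mean over all forms minus the mean over the 300 kept equals this share times the difference in mean score between dropped and kept patients. The documents say nothing about that difference, so neither its sign nor its size is known.

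**The case against.** The strongest reply on the version is that the plan probably means v2. The SAP cites a v2 licence, the protocol body names no version, and Appendix 1 is in English with distances in miles and blocks although the study is French, so it may be only illustrative. If v2 is administered, the domain and summary scores come from the software and not from Table 28, and what remains is an outdated appendix and some table rows. That is a fair reading, but it stays an inference: no passage states which form is handed to patients. Nor can Table 28 be set aside as a mere template, because Protocol 7.2.1 makes the table templates part of the SAP. A correction is needed on either branch.

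On the 300-form rule, the reply is that at the planned size it removes nothing. That stands. However, SAP 3.5.1 calls 300 an expected number, and the only ceiling stated for inclusion is 10 patients per hospital department, with 150 active physicians sought. More than 300 forms is possible, and only then does the rule have a function.

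It is also true that the SF-36 is only described. It enters neither regression in SAP 5.5.2.

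A reader might infer that SAP 5.5.3 contradicts itself, since it later promises results "for patients who have completed SF-36 questionnaire, total scores for each of the eight health domains" with no limit. That is weak: the sentence follows the 300-form rule and can be read as applying within those 300.

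**Conclusion.** Wrong as written. Protocol and SAP describe different SF-36 forms, the SAP's own item table is not consistent within Q9, and the SF-36 analysis set conflicts with the population rule. None of this is declared. The firm figure is 12 of 36 items with different response levels between Appendix 1 and Table 28, including all seven role items. It rests only on counting printed answer options.

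Three stronger conclusions are not supported:

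- That the study's SF-36 scores will be invalid. This follows only if the Appendix 1 form is the one completed, which the documents do not show.
- That the two versions differ on 12 items. The five Q9 differences may partly be drafting slips in Table 28.
- That the 300-form rule biases the results. It has no effect at 300 or fewer forms. Above that, the share dropped depends on an assumed number of returns, and the direction and size of any bias are unknown.

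The consequence is limited to one instrument for one secondary, descriptive objective. The point should still be settled before scoring.

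**What to change.** State in both documents which SF-36 version is administered. Align Appendix 1, every row of Table 28 (the Q9 block in particular) and the scoring algorithm to that version.

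Delete the 300-form rule. Score every returned form in the Analysis Population under the instrument's own missing-item rule, and report the numbers returned, completed and scorable so that the reader can see the denominator. List the version and analysis-set changes in SAP 5.6.

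The cost is text edits to the SAP and the appendix, and possibly the scoring of some additional forms if more than 300 come back. No new data collection is needed.

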5.5.4 Description of physician and patient characteristics

5.5.4.1 Description of physicians

The following physicians' characteristics will be described:

- Gender (Female/ Male)
- Number of years since medical school graduation ([APPENDIX](#))
- Investigator's medical specialty (Internal medicine/ Rheumatologist / Other).

A listing of other specialties will also be provided.

- Number of GCA cases (Horton) personally treated within the last year (prior to the date of inclusion of your first patient) (1-2 / 3-5/ 6-10/ 11-20/ >20)
- Investigator's main activity (University Hospital/ General Services Hospital/ Liberal activity)
- Investigator's activity location (Auvergne-Rhône-Alpes / Bourgogne-Franche-Comté / Bretagne/ Centre-Val de Loire/ Corse / Grand Est / Hauts-de-France / Île-de-France/ Normandie/ Nouvelle-Aquitaine / Occitanie / Pays de la Loire/Provence-Alpes-Côte d'Azur)

5.5.4.2 Description of patients

The following patients' characteristics will be described overall and by type of physician who follows the patient:

- Type of the patient's visit (Outpatient visit/Day hospital/ In-patient hospitalization)
- Age (years) as quantitative variable and in classes ([50 ; 70[/ ≥ 70) ([APPENDIX](#))
- Gender
- Weight at diagnosis (kg)
- Weight at inclusion (kg)
- Height at diagnosis (cm)
- Body mass index (BMI) (kg/m²) at diagnosis ([APPENDIX](#))
- BMI in classes (kg/m²) (<18.5 / [18.5 ; 25[/ [25.0 ; 30[/ ≥ 30) at diagnosis
- Smoking status (Smoker/ Former smoker/ Non-smoker ever / Unknown)
- Significant medical and surgical history and comorbidities (excluding those related / aggravated by the use of glucocorticoids according to the investigator's judgment and complications related to GCA (Horton) according to the investigator's judgment

- Significant medical and surgical history and comorbidities overall by MedDRA System Organ Class (SOC) and Preferred Term (PT)
- Significant medical and surgical history and comorbidities presented before the GCA (HORTON) diagnosis
- Significant medical and surgical history and comorbidities with ongoing specific treatment(s)

A listing of other significant medical and surgical history and comorbidities (excluding those related / aggravated by the use of glucocorticoids according to the investigator's judgment and complications related to GCA (Horton) according to the investigator's judgment) will be presented.

- Treatments administered by the patients at/after diagnosis of GCA (Horton)
 - Proportion of patients taking at least one treatment of Antiplatelets
 - Proportion of patients taking at least one treatment of Statins
 - Proportion of patients taking at least one treatment of Antiosteoporotic
 - Proportion of patients taking at least one treatment of Antihypertensives
 - Proportion of patients taking at least one treatment of Antidiabetics
 - Proportion of patients taking at least one treatment of Inhibitors of the proton pump
 - Proportion of patients taking at least one treatment of Hypnotics
 - Proportion of patients taking at least one treatment of Antidepressants
 - Proportion of patients taking at least one other treatment

- Concomitant treatments administered by the patients at diagnosis of GCA (Horton)
 - Proportion of patients taking at least one treatment of Antiplatelets
 - Proportion of patients taking at least one treatment of Statins
 - Proportion of patients taking at least one treatment of Antiosteoporotic
 - Proportion of patients taking at least one treatment of Antihypertensives
 - Proportion of patients taking at least one treatment of Antidiabetics
 - Proportion of patients taking at least one treatment of Inhibitors of the proton pump
 - Proportion of patients taking at least one treatment of Hypnotics
 - Proportion of patients taking at least one treatment of Antidepressants
 - Proportion of patients taking at least one other treatment

- Concomitant treatments at the out-patient/hospitalization visit of inclusion
 - Proportion of patients taking at least one treatment of the Antiplatelet agents family
 - Proportion of patients taking at least one treatment of Statins family
 - Proportion of patients taking at least one treatment of Antiosteoporotic family
 - Proportion of patients taking at least one treatment of Antihypertensive family
 - Proportion of patients taking at least one treatment of Antidiabetics
 - Proportion of patients taking at least one treatment of Inhibitor(s) of the proton pump
 - Proportion of patients taking at least one treatment of Hypnotics
 - Proportion of patients taking at least one treatment of Antidepressants
 - Proportion of patients taking at least one other treatment

A listing of other treatments will be presented.

